### *3.9. Timetable*

Recruitment of participants began on 19 October 2015 (for the study using tablet computers in antenatal clinics). Recruitment for the study using an app through a BYOD approach is expected to start in January 2017. Overall recruitment is expected to conclude on 31 December 2017.

## *4. Patient and Public Involvement*

For the tablet computers in antenatal clinics study, we will aim to recruit two pregnant women to advise us during the design and piloting of the survey questionnaires. We will also aim to involve these members of the public in the overall management of our study, and during the interpretation of our results. We will recruit them from the same general practices, midwifery services and hospitals where this study will be conducted. We will apply for the *Enabling Involvement Fund* offered by the Research Design Service London in order to reimburse these members of the public for travel expenses and their time.

For the app through a BYOD approach study, we will engage patients and the general public through our co-design sessions.

We expect that through patient and public involvement (PPI), we will be able to identify issues that are relevant to the target population so that our findings will become more relevant, and will have a more significant impact.

## 5. Regulatory Issues

### 5.1. Ethics approval

Ethics approval was obtained from the National Research Ethics Service (NRES) Committee South East Coast – Surrey.

### 5.2. Consent and withdrawal

Local research teams or CSOs will be responsible for taking written, informed consent at the participating general practices, midwifery services or secondary care sites. This will be done by adequately trained research or clinical staff using the documents *Antenatal mental health screening programme – Consent Form* (Version 1.1, dated 06 July 2015) or *mHealth for the EMA of mood during pregnancy – Informed Consent Form* (Version 1.2, dated 19 January 2017) as relevant. Participants will be given the opportunity to ask any questions prior to giving consent. In addition, participants will be made aware that they have at least 24 hours to decide whether or not they wish to take part in this study. However, if they wish to take part in the study, they will have the opportunity to consent immediately. Furthermore, the right of participants to withdraw will be clearly explained. Participants may withdraw at any stage without having to offer an explanation. Refusal to take part in any of these studies or withdrawing from them will not have an impact on the patients' legal rights, medical care or their relationship with those providing medical care.

### 5.3. Anonymity and Confidentiality

We will ensure the anonymity and confidentiality of the data collected from our participants through a number of steps. For the study using tablet computers in antenatal clinics, we will not collect personal identifiers from our participants. The data generated as part of this study will be stored in an anonymised database. This database will be hosted by the ICT Department at Imperial College London and will be located within the Imperial College London secure network. For this study, participant information will not be stored in any of the devices used for data collection (i.e., iPads); instead, these data will be transferred automatically to our secure database via a secure connection using secure socket layer (SSL) certificates.

For the study using an app through a BYOD approach, we will implement PIN authentication procedures and any data stored in participants' handsets will be encrypted. Transmission of data to our database will also take place via a secure connection using SSL certificates. We will implement two separate databases: (i) an anonymised database to store the data generated during the study, and (ii) a secondary database where we will store participants' details and their clinicians' details (which will be collected during the baseline assessment). The app will only need to connect to the anonymised database. The secondary database will be accessed by the researchers conducting this study, only in cases where a participant's EPDS score needs to be communicated to her clinician.

For both studies, access to the study databases will be restricted to researchers working on this project, and it will be enforced through administration of user rights and authentication of Imperial College London username and password.

## 5.4. Indemnity

Indemnity cover will be arranged through the Imperial College Joint Research Compliance Office (JRCO).

## 5.5. Sponsor

Imperial College London will act as the sponsor for this study.

## 5.7. Funding

The funding needs of this study have been met through the Imperial Biomedical Research Centre.

## 5.8. Audits and Inspection

This study may be subject to inspection and audit by the Joint Research Compliance Office under the remit as sponsor and other regulatory bodies to ensure adherence to Good Clinical Practice and the Research Governance Framework.

# 6. Study management

## 6.1. Data handling

We will ensure compliance with all the relevant NHS policies (i.e., Data Protection Policy, Freedom of Information Policy, Confidentiality Policy, Information Security Policy, Document and Records Management Policy, Information Sharing Policy, and Information Governance Policy). In addition, we will comply with the Information Governance (IG) policies of participating general practices, midwifery services or hospitals, as well as with the principles of IG outlined by the NHS Health Research Authority. In addition, we will observe all the relevant ICL policies (i.e., Data Quality Policy, and Information Systems Security Policies). Lastly, all the staff involved in this project will complete the Good Clinical Practice (GCP) training provided by ICL, and the IG training provided by the NHS.

## 6.2. Data Storage

We will keep one master file for signed consent forms. This file will be kept in a locked cabinet located in a secure room at the Department of Primary Care and Public Health, Imperial College London (ICL), [name]. Access to this room will be restricted to members of the research team working on this project.

We will not store participants' responses in the iPad devices used for the tablet computers in antenatal clinics study; instead, their responses will be transferred to a secure, anonymised database hosted in the ICL secure network. Data will be transmitted over a secure connection with Secure Socket Layer (SSL) certificates.

Data relevant to this study will be anonymised and stored in a secure database hosted by the Information and Communication Technologies (ICT) Department at ICL and located within the ICL secure network. This database will be encrypted using an AES 256 certificate (or equivalent). Access to

this database will be limited to ICL staff members working on this research project, which will be controlled through a policy of authorised usernames and passwords.

We will not store any personal identifiers for our participants in the study using tablets in antenatal clinics. For the study assessing an app through a BYOD approach, we will keep a secondary database containing participants' and their clinicians' contact details. This database will only be accessed if a participant's EPDS score needs to be communicated to her clinician.

No personal equipment will be used throughout the duration of this study.

After concluding this study, we will archive all data for up to 10 years according to Imperial College London policies.

### 6.3. Sensitivity issues

It is possible that participants with no previous history of common mental health disorder might receive a score highly suggestive of depression or anxiety. In these cases, we will ensure that patients are referred to the relevant mental health services linked to participating general practices, midwifery services or hospitals.

### 6.4. Dissemination plan and publication policy

The findings from different stages of this study formed part of [name]'s and will form part of [name]'s PhD Theses. One of the study protocols has been published in the BMJ Open ([name], [name], [name] et al. 2016), and we will submit another study protocol for publication in the BMJ Open, Journal of Medical Internet Research (JMIR Research Protocols ([www.researchprotocols.org](http://www.researchprotocols.org)) or similar journals. The findings of these studies will be disseminated through papers submitted to academic peer-reviewed journals, presentations and posters submitted to professional and academic conferences, and discussion with peers.

### 6.5. Future research

With these studies we expect to demonstrate the feasibility of implementing NICE guidelines for antenatal mental health care in general practices or midwifery services using tablet computers, and the feasibility of using a BYOD approach to support at-home collection of patient self-reported data. We also expect to ensure that the electronic administration (through iPads) of the EPDS does not affect the psychometric properties of this instrument. In addition, we will explore factors that affect patient engagement with longitudinal, repeated data collection.

The results from these studies will answer key questions about the impact of mobile technology on the quality of clinical data. These findings will inform a clinical trial evaluating the cost-effectiveness of mobile-based depression screening and monitoring in the UK, including its potential impact on clinical outcomes (i.e., postpartum depression). In addition, we will use these findings to inform a clinical trial led by the Nanyang Technological University in Singapore.

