Concerning the first aim, this study will evaluate the positive predictive value (PPV), the negative predictive value (NPV), and the false omission rate (FOR) of the Whooley questions (as recommended by NICE). In addition, this study will assess if the findings from the survey methodology literature (Wells, Bailey & Link 2014; Mavletova & Couper 2014) are relevant to validated screening instruments in clinical settings. Therefore, we will assess the impact that iPads as a delivery mode and survey questionnaire layout (i.e., scrolling versus paging) could have on the quality of the responses given to the Whooley Questions and the Edinburgh Postnatal Depression Scale (EPDS) when completed in the waiting area of general practices, midwifery services or secondary care sites prior an antenatal appointment. PPV, NPV and FOR will be assessed by comparing the answers given to the Whooley questions against women's scores on the EPDS. Data quality will be defined in terms of data equivalence (i.e., distribution of overall survey questionnaire scores) between the two layouts (i.e., scrolling and paging) of the EPDS. We will also compare the two layouts (i.e., scrolling and paging) in relation to: (i) acceptability to pregnant women; (ii) the time required to complete survey questionnaires; and (iii) data completeness. We will document the changes made to the original version of the EPDS during its adaptation for use with an app, and we will log the problems experienced by our participants while completing this screening tool. The latter has significant implications for the implementation of screening programmes, as it can pose an additional administrative burden to already busy staff members.

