## 3. Methods

### 3.1. Study Design

We will use a parallel, randomised control trial (RCT) study design. For the study assessing the use of tablet computers in antenatal clinics, participants will be randomly assigned to complete (i) an app version of the Whooley questions and the EPDS in which the questionnaires are presented using a scrolling layout (i.e., App screening – Scrolling), or (ii) an app version of the Whooley questions and the EPDS in which the questionnaires are presented using a paging layout (i.e., App screening – Paging).

Participants will also be asked if they wish to take part in the study evaluating an app through a BYOD approach. Those consenting to take part in this study will be randomly assigned to (i) complete the EPDS once a month for 6 months (i.e., retrospective assessment), or to (ii) complete the EPDS, plus 4 days of EMA of mood, sleep, worry, enjoyment and energy, plus EPDS once a month for 6 months (i.e., retrospective plus momentary assessment).

In selected sites, we will recruit an additional 30 participants into the app through a BYOD approach study. Participants recruited from these sites will receive feedback on their data from designated members of the clinical team.

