### 3.4.3. Mobile devices

For the assessment of tablet computers in antenatal clinics, we will use iPads to deliver the survey questionnaires. For the assessment of an app using a BYOD approach, we will use any tablet computer to collect the baseline assessments, and any Android or iOS handset to install the bespoke app.

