### **3.5.2.1.1. *App Screening – Scrolling layout***

Participants allocated to this intervention arm will receive an iPad running the survey questionnaires (personal demographic information, Whooley questions, and EPDS). We will consider that a participant has started completing the survey questionnaires as soon as they press the button *Start* displayed on the screen. Immediately after, a screen will be displayed which will contain an outline of the survey questionnaires to be completed and basic instructions on how to complete them. In this experimental group each survey questionnaire will be presented on a single screen. Therefore, participants will need to scroll vertically in order to answer all the questions. They will be able to scroll up and down as they wish and to modify the answers to previous question as long as they do it before submitting their answers. However, once they have submitted their responses, a message acknowledging their participation will be displayed on the screen of the iPad Air and they will no longer be able to modify their answers. Validation procedures will ensure that participants will not be able to submit a survey with unanswered questions. Once the surveys have been completed, the participants will return the tablet to a member of the research team. Subsequently, the participant will be given printed material

containing additional information on maternal mental health, and a printed letter [*Antenatal mental health screening – Communicating results to the clinician*, version 1.0, dated 28 April 2015] with her score on the EPDS will be given to her clinician.

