### 3.5.2.1.2. App Screening – Paging layout

Participants allocated to this intervention arm will receive an iPad Air running the survey questionnaires (personal demographic information, Whooley questions, and the EPDS). We will consider that a participant has started completing the survey questionnaires as soon as they press the button *Start* displayed on the screen. Immediately after, a screen will be displayed which will contain an outline of the survey questionnaires to be completed and some basic instructions on how to complete them. In this experimental group each survey questionnaire will be presented using a paging layout. Therefore, participants will only see one question on the screen at any given time. They will need to select and submit their answer to the current question before being able to move on to the next question. Participants will not be allowed to re-visit already answered questions. Validation procedures will ensure that participants will not be able to submit an unanswered question. Once the surveys have been completed, the participants will return the tablet to a member of the research team. Subsequently, the participant will be given printed material containing additional information on maternal mental health, and a printed letter [*Antenatal mental health screening – Communicating results to the clinician*, version 1.0, dated 28 April 2015] with her score on the EPDS will be given to her clinician.

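### Both tablet-study arms use iPads, so the trial can estimate layout effects on EPDS scores but not the effect of iPad delivery or whether the EPDS's psychometric properties are preserved

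*Combined protocol and SAP*

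**What the plan says.** Three statements concern the effect of the device itself.

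- Section 1 (Background), in the paragraph on the first aim: "we will assess the impact that iPads as a delivery mode and survey questionnaire layout (i.e., scrolling versus paging) could have" on the quality of answers to the Whooley questions and the EPDS. Device and layout are listed as two separate influences.
- Section 6.5: "We also expect to ensure that the electronic administration (through iPads) of the EPDS does not affect the psychometric properties of this instrument".
- Section 6.5 again: "The results from these studies will answer key questions about the impact of mobile technology on the quality of clinical data".

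The design is narrower. Section 3.1 randomises between two app versions, one scrolling and the other "an app version of the Whooley questions and the EPDS in which the questionnaires are presented using a paging layout". Section 3.4.3 says: "For the assessment of tablet computers in antenatal clinics, we will use iPads to deliver the survey questionnaires". The arm descriptions agree: "Participants allocated to this intervention arm will receive an iPad running the survey questionnaires" (Section 3.5.2.1.1, scrolling) and "Participants allocated to this intervention arm will receive an iPad Air running the survey questionnaires" (Section 3.5.2.1.2, paging).

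The between-group analyses of the tablet study (Sections 3.8.2.4 to 3.8.2.7) compare scrolling with paging. The hypotheses in Section 2.1.3 at one point name paper rather than paging as the comparator to scrolling, but no paper arm is described anywhere.

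**The concern.** An effect of giving the EPDS on an iPad can be estimated only against women, or occasions, where it is given some other way. This plan has none. Nor does it plan an analysis that addresses psychometric properties.

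The plan itself gives reasons to take a shared effect seriously. Section 1 says that adapting a questionnaire for an app can create mode effects peculiar to apps, and that mode effects matter because screening results feed into diagnosis, referral and treatment decisions. One app feature, compulsory answering, is present in both arms (Section 3.3.1.1.7), so the layout contrast cannot isolate it.

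EPDS thresholds of 10 and 13 are applied to these scores, and Section 6.5 says the findings will inform later clinical trials. If iPad delivery moved scores in both arms alike, nothing in the tablet study would reveal it, while Section 6.5 as worded would allow the opposite conclusion.

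**Working it through.** **1. Is there a non-iPad EPDS anywhere?**

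| Source | How the EPDS is given |
|---|---|
| Tablet study, scrolling (3.5.2.1.1) | iPad |
| Tablet study, paging (3.5.2.1.2) | iPad |
| BYOD study, baseline (3.5.2.2) | Tablet supplied by the research team |
| BYOD study, follow-up (3.4.2, 3.5.2.2.1, 3.5.2.2.2) | App on the woman's own phone |

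There is no paper or interview administration, no crossover and no historical control.

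**2. What does the planned contrast estimate?** Let μ be the mean score on the original EPDS in these women, δ a shift from iPad delivery common to both layouts, and λ the effect of each layout.

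- Scrolling mean = μ + δ + λ(scrolling)
- Paging mean = μ + δ + λ(paging)
- Difference = λ(scrolling) − λ(paging)

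δ cancels. The documents give no value for it, so I assume a range of 0 to 4 points. With no layout effect, the expected difference is 0 for δ = 0, 1, 2, 3 or 4. The comparisons of women scoring 10–12 and 13 or more have the same limit: both arms carry the shift and there is no unshifted reference.

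**3. Would a larger sample help?** Inputs from Section 3.6: SD 4, margin 3, one-sided alpha 0.025, power 0.80, target at least 300. I assume equal allocation, 150 per arm.

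The plan's own figures first:

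- The 250 for predictive values reproduces: 30 / 0.12 = 250.
- The 126 for layout equivalence does not follow from the stated inputs. Per arm, 2 × [4 × (1.960 + 0.842) / 3]² = 27.9, so 28 per arm and 56 in total. A two-sided equivalence calculation gives 38 per arm, 76 in total. A total of 126 (63 per arm) is obtained with an unstated true difference of 1 point, or with a margin of 2. This is a side observation; nothing below depends on it.

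At 150 per arm:

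- SE of the layout difference = 4 × √(2/150) = 0.462
- 95% half-width = 1.96 × 0.462 = 0.91 points
- Power of two one-sided tests at margin 3 with no true difference = 2Φ(3/0.462 − 1.96) − 1, which is above 99.9%

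Layout equivalence could be shown almost with certainty while δ stays unknown. More women would shrink the 0.91 but add nothing about δ.

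**4. Is there a psychometric analysis?** Section 3.8 has no reliability, factor-structure or criterion-validity analysis of the EPDS. The PPV, NPV and FOR (Sections 3.8.2.1 to 3.8.2.3) judge the Whooley questions against an EPDS score of 10 or more, so they take the EPDS as valid rather than test it. Equal mean scores in two layouts do not establish unchanged psychometric properties, even between those layouts.

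**The case against.** The strongest reply is that these statements lie outside the plan's formal inference. The aim in Section 2.1, the objectives in 2.1.1 and 2.1.2, the endpoints in 3.3.1.1 and the tests in 3.8.2 cover feasibility, the Whooley predictive values and scrolling versus paging. None promises a comparison of iPad with another mode. The psychometric sentence is an expectation under a Future research heading, and Section 1 goes on to define data quality as equivalence between the two layouts. All of this stands, and it limits the point to narrative claims. It does not remove it: Section 1 still states the delivery-mode assessment as study work, and defining quality by layout leaves that aim without a measure.

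Section 1 also uses the term delivery mode effect broadly enough to include layout decisions. That is fair, but the sentence at issue lists iPads and layout separately, and the broader usage does nothing for the psychometric claim.

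The absence of a paper arm may be deliberate, since the team's earlier systematic review is reported as finding app responses equivalent to other modes in clinical settings. That is a reason for studying layout. It is outside evidence, however, and Section 6.5 credits the answer to these studies.

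A reader might infer that the trial says nothing about iPad delivery. The documents do not support that: breakoff and its reasons, completion time and help requests are recorded, and they describe feasibility without a comparator. A reader might also infer from the two arm descriptions that the arms use different iPad models. The scrolling section itself later refers to an iPad Air, so the text does not establish a difference.

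**Conclusion.** The point holds as an overclaim in Sections 1 and 6.5. The tablet study identifies the effect of layout on EPDS scores among iPad users. It does not identify a score shift common to both layouts, of any size and at any sample size, and it contains no analysis bearing on the psychometric properties of the EPDS. This rests on the arms and devices as described in Sections 3.1, 3.4.3 and 3.5.2.1. The figures of ±0.9 points and power above 99.9% assume 150 per arm, SD 4 and, for the power, no true layout difference; the conclusion does not depend on them.

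Two stronger readings are not supported. The layout comparison and feasibility aims are not invalidated by this point. Nor do the documents say that similar means would be published as proof that iPad use leaves EPDS scores unaffected; the concern is that the present wording permits it. The paper comparator in Section 2.1.3 is not evidence of a third arm: it conflicts with Section 3.1, and no paper administration is described.

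**What to change.** - **Section 1:** restrict the response-quality aim to the effect of layout among women using iPads, and say that iPad delivery itself will be described for feasibility only.
- **Section 6.5:** delete the sentence on psychometric properties, and restrict the sentence on the impact of mobile technology to layout effects and feasibility.
- **Section 2.1.3:** reconcile the paper comparator with the scrolling and paging arms of Section 3.1.
- **Section 3.8.2.4:** add a sentence along these lines: the comparison of scrolling and paging will not be interpreted as evidence that the iPad EPDS is equivalent to the paper EPDS.

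The cost is a narrower conclusion. Recruitment, randomisation, data collection, sample size and tests are unchanged, and no further arm is requested.
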